11.8 Safety Analyses

Most safety analyses will be performed on the safety analysis population based on subject's actual treatment received.

A listing of planned summaries and analyses evaluating hypoglycemic events along with corresponding analysis plan section references is provided in Table 6.

Table 6: Listing of hypoglycemic event summaries and analyses

Analysis description	Section Reference	Tables Associated
1. Retrospective Summary of Continuous Glucometer Monitoring (CGM): Hypoglycemia Events	Section 11.7.3.1	Table 14.3.3.4.1
2. Retrospective Analysis of Continuous Glucometer Monitoring (CGM): Time in Hypoglycemia/Hyperglycemia	Section 11.7.3.2	Table 14.3.3.4.2
3. Overall Summary of Treatment-Emergent Adverse Events	Section 11.8.1	Table 14.3.2.1
4. Hypoglycemic Treatment-Emergent Adverse Events by Preferred Term	Section 11.8.1	Table 14.3.2.5

Analysis description	Section Reference	Tables Associated
5. Hypoglycemic Treatment-Emergent Adverse Events by System Organ Class, Preferred Term, and Maximum CTCAE Grade (based on lowest blood glucose values measured by fingerstick or venous blood draw)	Section 11.8.1.1	Table 14.3.2.6.1
6. Hypoglycemic Treatment-Emergent Adverse Events by System Organ Class, Preferred Term, and Maximum CTCAE Grade (based on lowest blood glucose values measured by test method equal "Other")	Section 11.8.1.1	Table 14.3.2.6.2
7. Hypoglycemic Treatment-Emergent Adverse Events by System Organ Class, Preferred Term, and Maximum ADA Grade (based on lowest blood glucose value measured by fingerstick or venous blood draw)	Section 11.8.1.1	Table 14.3.2.6.3
8. Hypoglycemic Treatment-Emergent Adverse Events by System Organ Class, Preferred Term, and Maximum ADA Grade (based on lowest blood glucose values measured by test method equal "Other")	Section 11.8.1.1	Table 14.3.2.6.4
9. Severe Hypoglycemic Treatment-Emergent Adverse Events by Preferred Term	Section 11.8.1	Table 14.3.2.7
10. Serious Hypoglycemic Treatment-Emergent Adverse Events by Preferred Term	Section 11.8.2	Table 14.3.2.13
11. IP-Related Serious Hypoglycemic Treatment-Emergent Adverse Events by Preferred Term	Section 11.8.2	Table 14.3.2.14
12. Summary of Hypoglycemic Treatment-Emergent Adverse Events	Section 11.8.1	Table 14.3.3.2.17
13. Summary of Symptomatic or Measured Hypoglycemic Treatment-Emergent Adverse Events by Site	Section 11.8.1.1	Table 14.3.3.2.18
14. Analysis of Hypoglycemic Treatment-Emergent Adverse Events	Section 11.8.1	Table 14.3.3.2.19
15. Summary of Reported ADA Hypoglycemic Treatment-Emergent Adverse Events	Section 11.8.1.1	Table 14.3.3.2.20
16. Overall Summary and Analysis of Treatment-Emergent Adverse Events by ERIPD Subgroup in SS, PPS2, and PPS3		Table 14.3.2.21; 14.3.2.22; 14.3.2.23; 14.3.2.24
17. Maximum Post-baseline Fasting Glucose CTCAE Grade	Section 11.8.3.1	Table 14.3.3.4.16

11.8.1 Treatment Emergent Adverse Events

An overall summary of TEAEs (defined in Section 7.3) will be presented, including the number of events reported, the number and percentage of subjects with at least one of the following (Table 6, Analysis 3):

- Adverse event
- Grade ≥ 3 TEAE
- Hypoglycemic TEAE
- Severe hypoglycemic TEAE
- IP-related AE

Sponsor: Gan & Lee Pharmaceuticals, USA Corporation
Protocol no: GL-GLAT2-3002

Statistical Analysis Plan
Version Date: 16-Nov-2020

- Grade \geq 3 IP-related AE
- Death
- SAE
- IP-related SAE
- Hypoglycemic SAE
- AE leading to discontinuation of IP
- IP-related AE leading to discontinuation of IP

To evaluate the potential impact of eligibility related important protocol deviations on subject safety, an overall summary of TEAEs will also be presented by presence / absence of ERIPD. ERIPDs are those coded to the Inclusion Criteria or Exclusion Criteria categories (refer to Section 7.1, 11.3 and Appendix 4 for details). Additionally, safety analyses of ERIPD interaction with treatment group will be performed in logistic regression models adjusted by country. The interaction term estimates, 90% CI and p-value from these interaction analyses will be presented with the number and percentage of subjects with the following TEAEs by presence / absence of ERIPD under each treatment arm:

- Adverse event
- Grade \geq 3 AE
- Hypoglycemic AE
- Severe hypoglycemic AE

A fragment of the SAS code for the interaction analysis is provided below for reference.

```
proc logistic data=<data>;
  class trt ERIPD/ param=ref ref='Lantus';
  model response=trt ERIPD trt*ERIPD;
run;
```

A breakdown of the number and percentage of subjects reporting each AE, categorized by System Organ Class (SOC) and preferred term coded according to MedDRA, will be presented. Note that counting will be by subject (not event), and subjects are counted only once within each SOC or preferred term. Sorting will be in descending frequency for SOC and descending frequency for preferred term within SOC in the total column.

A summary of events reported, categorized by maximum National Cancer Institute Common Terminology Criteria for Adverse Events (NCI CTCAE) severity grade as reported in the CRF will also be provided. Subjects with multiple events within a particular SOC or preferred term will be counted under the category of their most severe event within that SOC or preferred term. Sorting will be in descending frequency for SOC and descending frequency for preferred term within SOC in the total column.

Subject incidence of the following TEAEs will be tabulated by preferred term in descending order of frequency in the total column:

- Grade \geq 3 AEs
- Hypoglycemic AEs
- Severe hypoglycemic AEs
- IP-related AEs
- Grade \geq 3 IP-related AEs
- AE leading to discontinuation of IP
- IP-related AE leading to discontinuation of IP
- Injection site reactions

Sponsor: Gan & Lee Pharmaceuticals, USA Corporation
Protocol no: GL-GLAT2-3002

Statistical Analysis Plan
Version Date: 16-Nov-2020

A forest plot of the difference in incidence rates and CIs of TEAEs preferred terms with a $\geq 5\%$ difference in incidence between groups will be summarized. The 90% CIs will be computed using Wald method for risk difference without continuity correction.

Additionally, the hypoglycemia event rate will be compared between treatment groups using a negative binomial regression model (Table 6, Analysis 14). The response variable in the model will be the number of hypoglycemia events. The model will include factors for treatment group and site. In this study, sites were found to use variable procedures in their determination, collection and recording of the number of hypoglycemia episodes for individual subjects. So, to account for this additional variation, SITE is planned to be included as a fixed factor in the negative binomial regression model. This model will allow estimation of the site-adjusted, two-sided, 95% confidence interval of the treatment contrast. If that CI includes zero, we will conclude that this study does not provide sufficient evidence that subjects on this biosimilar have different numbers of hypoglycemic episodes compared to those on the reference analogue. The logarithm (to base e) of the follow-up time will be used as an offset variable in the model to adjust for subjects having different exposure times. The estimated treatment effect and the corresponding 95% confidence interval (CI), as well as the 2-sided p-value will be presented.

A sample SAS code fragment is provided below for reference:

```
proc genmod data = <data>;
    class trt site;
    model count = trt site / dist = negbin offset = time_log;
    lsmeans trt / ilink diff exp cl;
run;
```

All TEAEs will be listed for subjects in the Safety Analysis Set. A listing of all TEAEs leading to discontinuation of IP will be provided.

All non-treatment-emergent AEs recorded on the CRF will be listed separately for all screened subjects.

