## 1. SYNOPSIS

NAME OF SPONSOR: Gan & Lee Pharmaceuticals USA		PROTOCOL No.: GL-GLAT2-3002
NAME OF STUDY TREATMENT: Gan & Lee Insulin Glargine Injection		
TITLE OF STUDY: An Open-label, Randomized, Multicenter, Phase 3 Study to Compare the Immunogenicity, Efficacy, and Safety of Gan & Lee Pharmaceuticals Insulin Glargine Injection to Lantus® (Insulin Glargine Injection) in Adult Subjects with Type 2 Diabetes Mellitus		
STUDY CENTERS: Approximately 65 sites are planned in the United States		
STUDY PERIOD: Subjects randomized to the Gan & Lee Insulin Glargine Injection group and the Lantus® group will receive treatment for 26 weeks.		PHASE OF DEVELOPMENT: Phase 3
PLANNED STUDY DATES: The study started in 2017 and is expected to end in 2019		
OBJECTIVES: Primary Objective: 
 
To evaluate equivalence of Gan & Lee Insulin Glargine Injection and Lantus® in terms of immunogenicity
 
 Secondary Objectives: 
 
Immunogenicity: To evaluate the percentage of subjects with negative anti-insulin antibodies (AIA) at baseline who develop confirmed positive AIA up to visit Week 26, the percentage of subjects with at least a 4-fold increase in titers compared to baseline value, mean change from baseline in AIA titers between treatment groups, the percentage of subjects with confirmed positive AIA who develop any anti-insulin neutralizing antibodies up to visit Week 26, and the percentage of subjects in each treatment group with confirmed positive AIA up to visit Week 26
 
Safety: To evaluate the safety of Gan & Lee Insulin Glargine Injection in comparison with that of Lantus®
 
Efficacy: To evaluate the efficacy of Gan & Lee Insulin Glargine Injection in comparison with that of Lantus®
 
 Exploratory Objective: 
 
To investigate the retrospective hypoglycemic rate and time in hypoglycemia and hyperglycemia using continuous glucose monitoring (CGM) data
 
		

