5.1 Sample Size and Power

Enrollment was planned for 550 subjects overall (275 subjects per treatment group). The primary analysis for immunogenicity primary endpoint was to be an equivalence test for the difference in proportion of subjects who develop treatment-induced AIAs between Gan & Lee insulin Glargine Injection and Lantus® using the 2 Wald one-sided tests (TOST) approach with $\alpha=0.05$ (Chow and Shao 2002 (1)). After scientific and regulatory review, the method to evaluate immunogenicity equivalence will be the 90% confidence intervals of risk difference from logistic regression analysis (see Section 3.1). Under this newly adopted approach, no power loss is expected.

This sample size of 275 subjects per treatment group was chosen to achieve over 80% power using the TOST equivalence test for two proportions, a risk difference of zero and equivalence margins dependent on the observed treatment-induced AIA rate per Table 3 below. For example, a sample size of 550 will provide approximately 85% power for the TOST equivalence test using a treatment-induced AIA rate of 30% and a margin of 12% (See Table 3). The treatment-induced AIA is defined as newly confirmed positive AIA development or important (at least a 4-fold) increase in AIA titers, after baseline and up to visit Week 26 (see the definition of Primary Endpoint in Section 6.1 and Section 7.2). No drop outs are considered in the calculation. A larger than expected early discontinuation rate was observed as part of study monitoring activities and therefore protocol amendment 3 approved on 25-Apr-2019 included procedures to encourage subjects to return for assessments even if they have discontinued treatment early.

The appropriate similarity margin, based on the actual observed event rate for the intended reference product, will be used for final analysis after database lock as summarized in the Table 3 below. The power calculation in the table was adapted for a sample size of 550 using the treatment-induced AIA rate for the reference product. Linear interpolation will be used for values between AIA rates in the table.

Sponsor: Gan & Lee Pharmaceuticals, USA Corporation
Protocol no: GL-GLAT2-3002

Statistical Analysis Plan
Version Date: 16-Nov-2020

Table 3: Similarity margins for actual observed event rate of proposed biosimilar to insulin glargine for various immunogenicity event rates

Treatment-induced AIA Rate for the Reference Product	Margin	Power
10%	7.9%	83%
15%	9.3%	83%

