Equivalence in difference in proportion δ between Gan & Lee Insulin Glargine Injection (π_1) and Lantus® (π_2) will be tested by comparing the limits of the 90% CI for treatment-induced AIA development with the following null hypothesis:

$$H_0: (\pi_1 - \pi_2) \leq -\delta_0 \text{ or } (\pi_1 - \pi_2) \geq \delta_0$$

Against the alternative hypothesis of:

$$H_1: -\delta_0 < (\pi_1 - \pi_2) < \delta_0$$

where δ_0 is the margin dependent on the observed unadjusted treatment-induced AIA rate in Lantus® (π_2) and is defined in Section 5.1, Table 3.

To evaluate equivalence of Gan & Lee Insulin Glargine Injection to Lantus® the calculated 90% CI has to be entirely contained with the interval $(-\delta_0, \delta_0)$.

A sample SAS code fragment is provided below for reference:

```
proc logistic data=<data>;
    class trt / param=ref ref='Lantus';
    model response=trt;
run;
```

The Fisher scoring algorithm will be used for maximum likelihood estimation of the regression parameters. The difference in proportions along with the corresponding 90% CI in the SS using a logistic regression model will be calculated. The delta method will be used to calculate the standard error for the difference and the associated confidence interval (Ge M, Durham LK, Meyer RD 2011 (4)).

Subjects were randomly assigned to treatment using variable block size (See Section 5.2). Blocking should be taken into account when the intra-block correlation is non-zero (Matts and Lachin 1988 (5)). An intra-block correlation of zero can be safely ignored in the analysis (Efird 2011 (6)). Subjects are generally anticipated to remain within sites so the intra-block correlation within investigative site can be assumed to be zero and therefore no adjustment for block is planned.

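### The treatment-by-ERIPD safety model gives a meaningless interaction estimate, CI and p-value whenever an arm-by-ERIPD cell has no events, and its country adjustment cannot operate in a US-only trial

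*SAP*

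**What the plan says.** SAP 11.8.1 wants to know whether enrolling subjects who breached an eligibility criterion affected safety. It states that "safety analyses of ERIPD interaction with treatment group will be performed in logistic regression models adjusted by country". The outcomes are any AE, Grade ≥3 AE, hypoglycemic AE and severe hypoglycemic AE. "The interaction term estimates, 90% CI and p-value from these interaction analyses will be presented", together with the number and percentage of subjects with each event by ERIPD status in each arm.

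The reference PROC LOGISTIC fragment contains "model response=trt ERIPD trt*ERIPD". It has no country term, no Firth option and no exact statement. The SAP gives no rule for empty or sparse cells. The only estimation method it names for any logistic model is in 11.6.1.1, for the primary endpoint: "The Fisher scoring algorithm will be used for maximum likelihood estimation of the regression parameters".

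On geography, the Protocol synopsis says "Approximately 65 sites are planned in the United States". No other country is named for sites.

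**The concern.** There are two separate problems.

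**Separation.** Severe hypoglycemia is likely to be the rarest of the four outcomes. Protocol 8.4.2 excludes brittle diabetes, giving third-party-assisted hypoglycemia as an example. The events are then spread over four cells, two of which (the ERIPD cells) may be small. When a cell has no events, the maximum-likelihood interaction does not exist as a finite number. The software still prints an estimate, a very wide interval and a Wald p-value. That p-value is large however strongly the cells differ, so it carries no information about the interaction.

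**Country.** A covariate with one level cannot adjust anything. The text and the code also disagree on whether it is in the model.

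At stake is the usefulness of a check that the SAP added in order to judge the effect of ineligible enrollment on safety.

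**Working it through.** The documents give no event count, rate or power for this analysis, so there is no figure of theirs to reproduce.

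**Inputs.** 275 subjects per arm (SAP 5.1). Model: treatment, ERIPD and their interaction (SAP 11.8.1). One country (Protocol synopsis). The severe-event rate and the ERIPD share are not given; both are assumptions below.

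**1. Country.** Adding a constant column to the four-column model matrix gives rank 4 out of 5 columns. The term adds nothing and biases nothing.

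**2. What an empty cell does.** The model is saturated, so the interaction is a difference of two log odds ratios. Assumed illustration: without ERIPD, 3/247 in each arm; with ERIPD, 6/28 on test product and 0/28 on Lantus.

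- Maximum likelihood: the non-ERIPD log odds ratio is 0, and the ERIPD one is log(6/22) − log(0/28), which is infinite. Under Fisher scoring the estimate grows by about 1 per iteration:
  - iteration 8: 7.9, SE 18.9, z = 0.42, p = 0.68
  - iteration 12: 11.9, SE 139, z = 0.086, p = 0.93
  - iteration 20: 19.9, SE 7,596, z = 0.003, p = 0.998
- Likelihood-ratio test on the same data: p = 0.017.
- Firth (equivalent here to adding 0.5 to events and to non-events in each cell): log(6.5/22.5) − log(0.5/28.5) = −1.24 + 4.04 = 2.80. The penalized likelihood-ratio p is 0.046 when the null fit keeps the full model's penalty, and 0.061 when it uses the reduced model's penalty. The Firth Wald p is 0.10.

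Other assumed patterns at 20% ERIPD (220, 220, 55, 55 subjects). Events are in the order Lantus without ERIPD, test without, Lantus with, test with:

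| Events | ML Wald p at convergence | Comparators |
|---|---|---|
| 3, 3, 0, 8 | 0.993 (estimate 17.4, SE 1,994, 90% CI about −3,262 to 3,297) | likelihood ratio 0.010; exact conditional 0.046 |
| 6, 1, 0, 6 | 0.992 | likelihood ratio 0.0004; exact conditional 0.004 |
| 3, 3, 0, 2 | 0.994 | exact conditional 0.46 |
| 3, 3, 1, 5 (no empty cell) | 0.22 (estimate 1.69) | likelihood ratio 0.20; exact conditional 0.29 |

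The model behaves normally once every cell has an event. With an empty cell, p is about 0.99 whether the data show a strong contrast (second row) or almost none (third row).

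**3. How likely is an empty cell?** With event rate q in all cells, ERIPD share s, n1 = 275s and n0 = 275(1 − s):

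P = 1 − {[1 − (1 − q)^n1] × [1 − (1 − q)^n0]}²

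For q = 1%, s = 5%: n1 = 13.75, n0 = 261.25; (0.129 × 0.928)² = 0.014; P = 0.986. For q = 5%, s = 30%: n1 = 82.5, n0 = 192.5; (0.985 × 1.000)² = 0.971; P = 0.029.

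| ERIPD share | q = 1% | 2% | 3% | 5% |
|---|---|---|---|---|
| 5% | 99% | 94% | 88% | 74% |
| 10% | 95% | 82% | 68% | 43% |
| 20% | 86% | 56% | 34% | 12% |
| 30% | 77% | 37% | 16% | 3% |

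**The case against.** A reader might infer that a real safety signal would be passed off as reassurance. The documents do not support that. The same sentence of 11.8.1 puts the cell counts beside the p-value, so 6/28 against 0/28 would be visible, next to an interval running into the thousands. No alpha or decision rule is attached to this interaction, whereas the negative binomial model in the same section does have one. Hypoglycemic events are also listed individually and summarized by ERIPD subgroup (11.8.1.1 and Table 6, Analysis 16).

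A reader might also take the probability table as the chance of missing a signal. It is not. It assumes equal rates everywhere, so there is no interaction to miss; it measures only how often the printed output would be uninterpretable. With 3, 3, 0, 2 events, a valid method is non-significant too. Harm needs an empty cell and a one-sided cluster together, and the documents allow no probability for that.

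The ERIPD share may not be small. SAP Appendix 4 codes BMI above 35 kg/m² as an eligibility deviation, while the Protocol admits up to 45 kg/m²; hence the 30% row. Section 11.8.1 does not say which severe is modelled, although SAP 7.3 warns against confusing ADA severe with CTCAE Grade 3, and the rate depends on that choice. The code is offered for reference only, and its CLASS statement gives ERIPD the reference level Lantus, so it is evidently not final.

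All of this limits the weight of the point. It does not rescue the output: visible counts do not make a divergent estimate, its CI and its p-value worth reporting.

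**Conclusion.** The point holds in a limited form. As specified, the severe-hypoglycemia interaction is uninterpretable whenever an arm-by-ERIPD cell is empty. How likely that is rests entirely on assumed rates: about 99% at a 1% rate with 5% ERIPD, about 3% at a 5% rate with 30% ERIPD. A p-value near 1 from such a fit must not be read as absence of interaction. Separately, the country adjustment is inoperative and contradicts the SAP's own code; it causes no bias but should not stand. The analysis is supportive, and nothing in the primary or key secondary testing depends on it. The change is worth making because the plan commits to printing these numbers and the correction is small.

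**What to change.** In SAP 11.8.1:

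- Delete the adjustment by country.
- For severe hypoglycemic AEs and Grade ≥3 AEs, fit the interaction with Firth's penalized likelihood. Report the profile-likelihood 90% CI and the penalized likelihood-ratio p-value, not Wald results. Name the penalty used in the null fit, since it moved p from 0.046 to 0.061 in the illustration. Exact conditional logistic regression is an acceptable alternative.
- State whether severe means ADA severe or CTCAE Grade 3.
- Put no site term in place of country. The same section does report that "sites were found to use variable procedures in their determination, collection and recording of the number of hypoglycemia episodes for individual subjects", which makes a site term tempting. But 550 subjects over about 65 sites is about 8.5 per site, roughly four per arm, and SAP 11.1 pools only sites with fewer than 8. A site term would bring the sparse cells back.

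The cost is a sentence or two of SAP text and one model option, before database lock. The downside is that Firth estimates are shrunk slightly toward zero.

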5.2 Randomization

Subjects will be randomly assigned in a 1:1 ratio to Gan & Lee Insulin Glargine Injection or Lantus® treatment. Subject randomization will use a randomly permuted block design with varying block sizes and without stratification.

Registration and randomization will take place using a centralized Interactive Web Response System (IXRS). At registration, the IXRS will assign a unique subject identification number that will be used on all of that subject's eCRFs and serious adverse event (SAE) report forms.

This is an open-label study, however, to avoid the introduction of operational bias into final study results and to increase the interpretability and reliability of the data, certain roles of the Sponsor and study team will be blinded. Details are provided in the Data Blinding and Documentation of Aggregate Data Dissemination Plan (hereafter referred to as the Blinding Plan).

6. Endpoints and Covariates

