11.6.1.4 Multiplicity

Hierarchical testing strategy will be used to account for multiplicity. Equivalence in efficacy will only be demonstrated if equivalence in immunogenicity is demonstrated.

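### The adverse-event forest plot selects preferred terms on the same arm difference that its 90% intervals then estimate, so the displayed intervals exclude zero far too often and clear differences in rarer terms are not plotted

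*SAP*

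**What the plan says.** SAP 11.8.1 (Treatment Emergent Adverse Events) describes the figure in two sentences. The first sets the content and the inclusion rule: "A forest plot of the difference in incidence rates and CIs of TEAEs preferred terms with a $\geq 5\%$ difference in incidence between groups will" […]. The second sets the interval: "The 90% CIs will be computed using Wald method for risk difference without continuity correction".

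The only multiplicity provision is SAP 11.6.1.4. It says "Hierarchical testing strategy will be used to account for multiplicity" and then orders immunogenicity before efficacy. Adverse events are outside it.

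The same section also tabulates every preferred term by system organ class, as number and percentage per arm, with no threshold. It adds preferred-term tables for Grade 3 or higher, hypoglycemic, severe hypoglycemic, IP-related, discontinuation and injection-site events. SAP 11.8.2 tabulates serious and fatal events by preferred term. None of these tables is given an interval for the arm difference. The other safety models with intervals work at a different level: the eligibility-deviation interaction models use four broad event categories, and the negative binomial model compares hypoglycemia event rates.

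**The concern.** The filter and the estimate use the same number. If a term is shown only when the observed difference is at least 5 points, its 90% interval no longer has 90% coverage, because the samples in which the difference came out near zero have been removed. A reader of the plot would see a set of terms that mostly appear to differ between the products, even if the products were identical.

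The rule also works the other way. An absolute cut of 5 points is hard for an uncommon event to reach, so a lopsided split in a rarer term gets no interval anywhere.

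Comparing the safety of the two products is a stated secondary objective (Protocol 7.2.2), and this is the only planned preferred-term display with an interval for the arm difference. What is at stake is how readers interpret adverse-event imbalances, in both directions.

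**Working it through.** **Inputs.** Planned size: "Enrollment was planned for 550 subjects overall (275 subjects per treatment group") (SAP 5.1). Allocation: "Subjects will be randomly assigned in a 1:1 ratio" (SAP 5.2). The size of the Safety Analysis Set is not given, so 275 per arm is assumed, with 250 and 220 shown as a range. Selection rule and interval: SAP 11.8.1. The documents give no expected incidence for any preferred term, so results are shown over a range of incidences.

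**The plan's own figure.** The plot has no stated numerical result. As a check on the sample size, the TOST power in SAP 5.1 at a 30% rate and a 12% margin is 2Φ(0.12/SE − 1.645) − 1, with SE = √(2 × 0.30 × 0.70/275) = 0.0391. This gives 84.6%, against about 85% stated, so it reproduces.

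**Step 1: the smallest difference that is displayed.** 5% of 275 is 13.75, so a term needs a gap of 14 subjects (14/275 = 5.09 points).

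**Step 2: its 90% Wald interval**, d ± 1.645 × √(p₁(1−p₁)/275 + p₂(1−p₂)/275):

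| Subjects | Incidence | 90% CI (points) |
|---|---|---|
| 0 vs 14 | 0.0% vs 5.1% | 2.9 to 7.3 |
| 14 vs 28 | 5.1% vs 10.2% | 1.4 to 8.8 |
| 36 vs 50 | 13.1% vs 18.2% | 0.01 to 10.2 |
| 37 vs 51 | 13.5% vs 18.5% | −0.04 to 10.2 |
| 55 vs 69 | 20.0% vs 25.1% | −0.8 to 10.9 |
| 110 vs 124 | 40.0% vs 45.1% | −1.8 to 12.0 |

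The interval first includes zero at a mean incidence of (37 + 51)/550 = 16.0%. Below that, every displayed term has an interval that excludes zero, because at the same mean a larger difference lies further from zero and has a slightly smaller standard error. The corresponding limit is 15.0% at 250 per arm and 11.6% at 220 per arm.

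**Step 3: no true difference.** Exact enumeration over two independent Binomial(275, p) arms:

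| True incidence, both arms | P(displayed) | P(CI excludes 0, given displayed) | P(CI excludes 0), no selection |
|---|---|---|---|
| 5% | 0.8% | 100% | 10.1% |
| 10% | 5.5% | 100% | 10.3% |
| 15% | 10.7% | 93% | 10.2% |
| 20% | 15.0% | 67% | 10.1% |
| 30% | 20.9% | 49% | 10.2% |
| 40% | 24.0% | 44% | 10.5% |

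Coverage of the true value (zero), given display, is 100% minus the third column: 0% at 10% incidence, 33% at 20% and 56% at 40%, against a nominal 90%.

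**Step 4: what the plot omits.**
- 11 vs 1 subjects: difference 10/275 = 3.6 points, 90% CI 1.6 to 5.7. Not plotted.
- 13 vs 0 subjects: difference 4.7 points, 90% CI 2.6 to 6.8, Fisher exact p = 0.0002. Not plotted.
- True rates of 4% vs 1%: the 90% CI excludes zero in 76% of trials, but the term is plotted in only 8%.

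**Step 5: alternative selection rules**, with no true difference. A cut of at least 2% in either group still favours lopsided splits, since 6 vs 0 qualifies and 5 vs 5 does not. At a true 1% incidence, 35% of the terms it displays have an interval that excludes zero. A cut of at least 2% in both arms combined gives 9%. For terms at 5% to 40% incidence the combined cut shows essentially every term, and the figure is about 10%. Both examples in step 4 pass it (12/550 = 2.2%; 13/550 = 2.4%), and a true 4% vs 1% is plotted in 81% of trials.

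**The case against.** Several points against the concern stand.

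No decision rests on the figure. It has no test, p-value or conclusion rule, and the Protocol synopsis already says that safety variables are summarized descriptively. Labels and footnotes belong to the separate TFL shells (SAP Appendix 3), which are not available here. Hypoglycemia, the event of special interest, has its own unselected model with a 95% interval.

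A reader might infer that nearly every term in the plot will look significant by construction. The documents do not support that. The guarantee stops at a mean incidence of about 16% (about 12% at 220 per arm), and commoner terms are the ones most likely to pass the filter when the products are alike: 24% at 40% incidence against 0.8% at 5%. With no incidences in the documents, the share of displayed terms on each side of the limit is unknown.

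A reader might also infer that differences in rarer events go unreported. They do not. They are missing from the figure and have no interval, but the unfiltered tables give their counts and percentages.

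The strongest point is that selecting by incidence shows more chance findings, not fewer. Take an assumed 20 independent terms with no true difference (5 at 10% incidence, 5 at 8%, 10 at 5%). The planned rule displays at least one in about 42% of trials, whereas plotting all 20 shows at least one interval that excludes zero in about 88%. This mix and the independence are illustrative only. The comparison does not rescue the planned rule: with all terms shown, the reader can see how many exclude zero out of how many, and each interval has roughly its stated coverage. Under the planned rule neither is true.

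**Conclusion.** The concern holds as a defect of presentation in one descriptive safety figure. Selecting on the observed arm difference makes the nominal 90% intervals invalid for the terms shown. The exclusion of zero is automatic up to about 16% mean incidence. Above that it is still several times the nominal 10% when there is no true difference (67% at 20%, 49% at 30%, 44% at 40%). The plot also leaves out clear imbalances such as 11 vs 1 or 13 vs 0 subjects, which then have no interval in any planned preferred-term output.

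This does not touch the immunogenicity or HbA1c tests, and no adverse-event data are lost from the report.

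The figures assume 275 per arm in the Safety Analysis Set and independent binomial arms. A smaller set lowers the 16% limit but leaves the conclusion unchanged.

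**What to change.** In SAP 11.8.1, replace the 5-point difference criterion with an incidence criterion that ignores treatment arm: preferred terms reported by at least 2% of all subjects in the Safety Analysis Set, both arms combined, or another combined cut fixed before unblinding. Plot the risk difference and 90% CI for every such term. State on the figure that the intervals are descriptive and unadjusted for multiplicity. The cut should use combined incidence and not incidence in either group, for the reason in step 5 of the working.

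The cost is one phrase in the SAP, one filter in one figure program and a longer plot. About 1 in 10 terms with no true difference will show an interval that excludes zero by chance, and the figure note should say so. Any cut leaves something out: at 2% combined, a split of 8 vs 0 (8/550 = 1.5%) would still appear only in the tables.
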